10.3.4 Safety Follow-up

At the safety follow-up visit (Visit 20; Safety Follow-up, Week 52 ± 2 weeks), the following assessments will be performed:

- Review of concomitant medications/non-drug therapies
- AE monitoring
- sPGA, PASI, BSA evaluation
- Brief physical examination
- Vital signs (body temperature, pulse rate, blood pressure, and respiratory rate and measure body weight)
- PK and immunogenicity

- Clinical laboratory assessments (hematology and serum chemistry)
- Urinalysis
- Urine pregnancy test (female subjects of childbearing potential only)

The safety follow-up visit is done by subjects who completed the study treatment as per protocol requirements and those who have withdrawn from the study early.

If the subject does not show up to the clinical visit, the site should try contacting the subject by phone for at least 8 weeks after the scheduled follow-up visit and obtain information regarding the occurrence of adverse events, treatments for psoriasis as well as other concomitant medications and pregnancy status. In case the subject is a female of childbearing potential, at Week 48 a urine dipstick pregnancy test should be provided.

Information collected after Week 52 visit will be collected only as source data and not included in the eCRF.

At the safety follow-up visit the investigator should consider the next therapy to prescribe to the subject off-study, in order to maintain clinical benefit.

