12.1.2 Assessment of Adverse Events

For the purposes of this study, each non-serious untoward medical occurrence reported by a subject undergoing study-related procedure(s) before the first M923 or EU RPP treatment will be recorded on the AE eCRF; however, these events will not be considered as AEs and will not be included in the analysis of AEs.

Each treatment-emergent AE (non-serious AE or SAE) from the first M923 or EU RPP treatment until study completion/discontinuation (Week 48) or 4 weeks following the last M923 or EU RPP treatment (for early termination subjects) will be described on the AE eCRF using the medical diagnosis (preferred), or, if no diagnosis could be established at the time of reporting the AE, a symptom or sign, in standard medical terminology in order to avoid the use of vague, ambiguous, or colloquial expressions (see definition in [Section 12.1](#)). Each AE will be evaluated by the investigator for:

- Seriousness as defined in [Section 12.1.1.1](#)
- Severity as defined in [Section 12.1.2.1](#)

- Causal relationship to IP exposure or study procedure as defined in [Section 12.1.2.2](#)

For each AE, the outcome (ie, recovering/resolving, recovered/resolved, recovered/resolved with sequelae, not recovered/not resolved, fatal, unknown) and if applicable action taken (ie, dose increased, dose not changed, dose reduced, drug interrupted, drug withdrawn, not applicable, or unknown) will also be recorded on the AE eCRF. Recovering/resolving AEs will be followed until resolution, medically stabilized, or 30 days after the study completion/termination visit, whichever comes first. If the severity rating for an ongoing AE changes before the event resolves, the original AE report will be revised (ie, the event will not be reported as separate AE). During the course of any AE, the highest severity rating will be reported.

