^p The investigator or a qualified designee will evaluate the current injection sites 30 minutes (\pm 10 minutes) after study drug administration in the clinic at Weeks 0, 1, 17, 19, 21, 25, 27, 37, and 39. They should also evaluate any immediately prior injection site at each subsequent visit as applicable. For injections given at home, injection site reactions will be recorded in the subject diary. There will be no injection at Week 48 (Visit 19), but injection site evaluation for previous injections will occur.

^q The subject should bring the diary at all visits between Weeks 1 and 48. The investigator will review the diary for completeness, request missing information periodically and in a timely manner, photocopy and store the applicable pages in the source documents until the original diary is collected. At Week 25, the subject diary will be collected by the investigator and a new one will be provided until Week 48.

^r Visit windows are \pm 1 day at Visit 3, \pm 3 days for Visits 4-19 and \pm 2 weeks for Visit 20. Reference for visit windows/study day is scheduling based on Visit 2/Baseline Visit.

^s If the subject does not show up to the clinical visit, the site should try to contact the subject by phone for at least 8 weeks after the scheduled follow-up visit and obtain information regarding the occurrence of adverse events, psoriatic and concomitant treatments and pregnancy status. Discontinuing subjects will be invited to perform this visit 5 weeks after last IP dose.

Table 2
Laboratory Parameters

Panel	Parameters	
Hematology	Red blood cell count Hemoglobin Hematocrit Platelet count Mean cell volume White blood cell count (total leucocytes)	Neutrophils (absolute and %) Lymphocytes (absolute and %) Monocytes (absolute and %) Eosinophils (absolute and %) Basophils (absolute and %)
Serum biochemistry	Aspartate transaminase Alanine transaminase Alkaline phosphatase Gamma glutamyl transferase Total bilirubin Lactate dehydrogenase Creatine kinase C-reactive protein Cholesterol Triglycerides Total protein	Sodium Potassium Chloride Bicarbonate Urea Creatinine Albumin Calcium Phosphate Glucose Uric acid
Urinalysis	Leucocytes Protein Bilirubin Urobilinogen Glucose	Ketones Blood pH Nitrite Specific gravity
Urine microscopy	To be done where clinically indicated	
Viral serology	Hepatitis B surface antigen, anti-Hepatitis B surface antigen and anti-Hepatitis B core total (IgG and IgM)	Hepatitis C antibody Human immunodeficiency virus (HIV I and II)

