8.1 Adverse Events

Adverse events will be coded using the latest version of MedDRA.

Treatment-emergent adverse events (TEAEs) are defined as AEs that started or worsened in severity on or after the first dose of study medication, until study completion/withdrawal (Week 48) or 30 days following the last M923 or EU RPP treatment for early withdrawn subjects.

All TEAEs (including SAEs, AEs related to study drug, AEs leading to withdrawal, and injection site reactions) will be presented in summary tables. Summary tables shall indicate the number of subjects who experienced adverse events. In addition, tables will be prepared to list each AE, the number of subjects in each treatment arm who experienced an adverse event at least once, and the rate of subjects with AE(s). AEs will be grouped by system organ class and preferred term. Each event will then be divided into defined severity grades (mild, moderate, severe). The tables will also divide the AEs into those considered related (a “possibly related” or a “probably related” AE will be considered as a “related AE”) to the treatment and those considered unrelated (an “unlikely related” or a “not related” AE will be considered as an “unrelated” AE). In addition a summary of subject incidence of the top 5% of AEs will be produced.

All AEs for each subject, including the same event on several occasions, will be listed, giving both MedDRA preferred term and the original term used by the investigator, system organ class, severity grade, seriousness, relation to the treatment, onset date, and stop date.

AEs that occurred before first dose of study drug will be listed separately.

The clinical safety and tolerability of the transition from EU RPP to M923 as compared with continuous use of EU RPP with regard to AEs will be evaluated with a summary of all TEAEs by treatment arm and by treatment period:

- Period 1 from Week 0 to Week 16 (included)
- Period 2 from Week 16 to Week 25 (included)
- Period 3 from Week 25 to Week 37 (included)
- Period 4 from Week 37 to Week 48 (included)
- Follow-up

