The number and percentage of subjects with any AE, any related AE, any severe AE, any related severe AE, any SAE, and any related SAE, as well as the total number of events for each category, will be summarized by treatment group. The number of deaths due to an AE, hospitalization due to an AE and study discontinuation due to an AE will be summarized by treatment arm and analysis period (Arm A and B up to Week 16; Arm A, B1 and B2 after Week 16).

The number and percentage of subjects with an AE, as well as the total number of AEs, will be summarized for each treatment arm and analysis period (Arm A and B up to Week 16; Arm A and B2 after Week 16). This tabulation will be repeated by relationship and severity.

AEs that occurred before first dose of study drug will be listed separately. Any adverse events reported more than 30 days after a subject has completed or withdrawn early from the study, will not be summarized but will be listed.

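### SAP 8.1 defines TEAEs by onset date but removes late-reported AEs from the summaries by report date, so some in-window TEAEs, mainly in early leavers, would be listed but not tabulated

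*SAP*

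**What the plan says.** SAP 8.1 starts the TEAE window at the first dose and dates events by onset or worsening. The window runs "until study completion/withdrawal (Week 48) or 30 days following the last M923 or EU RPP treatment for early withdrawn subjects". The same section says that all TEAEs go into summary tables, with no condition on when they were reported, and plans a by-period TEAE summary that includes a follow-up period. Its closing paragraph then applies a different clock: "Any adverse events reported more than 30 days after a subject has completed or withdrawn early from the study, will not be summarized". The sentence ends by keeping such events in the listings.

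Three parts of the protocol bear on this:

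- **Follow-up of early leavers.** Section 10.6 plans their follow-up visit 5 weeks after the last dose, if they agree. The schedule in section 20.2 repeats it: "Discontinuing subjects will be invited to perform this visit 5 weeks after last IP dose".
- **Missed follow-up visits.** Section 10.3.4 has sites telephone the subject for at least 8 weeks after the scheduled visit, asking among other things about AEs. It then says: "Information collected after Week 52 visit will be collected only as source data and not included in the eCRF".
- **AE recording.** Section 12.1.2 requires each treatment-emergent AE to be described on the AE eCRF. For early terminations it ends the period 4 weeks after the last dose, where the SAP has 30 days.

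**The concern.** An event that began inside the TEAE window but was reported late must be tabulated under one sentence of SAP 8.1 and must not be under another. Following the later sentence literally undercounts TEAEs, because the rule can only remove events. It bears most on the time just after early discontinuation, where the follow-up visit is the only scheduled contact after the termination visit.

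The listing does not make the removal traceable. The fields that SAP 8.1 names include onset and stop dates but no report date, so a reader could not tell which listed events the rule had taken out of the tables.

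The eCRF restriction is a second, independent gap. Sites are told to ask about AEs by telephone, but answers obtained after the Week 52 visit stay out of the database from which tables and listings are made.

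**Working it through.** **Reproducing the plan's days.** Study day = 7 × week + 1 gives Week 16 = Day 113, Week 48 = Day 337 and Week 52 = Day 365, as both schedules state.

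**Other inputs.** Reporting cut-off: 30 days after completion or withdrawal (SAP 8.1). Early leavers' TEAE window: 30 days after last dose (SAP 8.1), or 4 × 7 = 28 days (Protocol 12.1.2). Early leavers' follow-up visit: 5 × 7 = 35 days after last dose (Protocol 10.6 and 20.2). Week 52 visit window: ± 14 days (Protocol 10.3.4 and 20.2). Telephone follow-up: at least 8 × 7 = 56 days (Protocol 10.3.4).

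**1. Early leavers.** Count from the last dose as day 0 and let withdrawal be recorded on day w. The cut-off is day w + 30. The day-35 visit is too late when 35 > w + 30, that is, when w < 5.

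| w | Cut-off (w + 30) | Visit, days after withdrawal (35 − w) | AE first reported at the visit |
|---|---|---|---|
| 0 | 30 | 35 | not summarised |
| 4 | 34 | 31 | not summarised |
| 5 | 35 | 30 | summarised |
| 14 | 44 | 21 | summarised |

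Example: withdrawal on day 2, onset on day 10, first reported on day 35. Onset is inside the window on either the 30-day or the 28-day version. The report comes 35 − 2 = 33 days after withdrawal, so the event is a TEAE that is listed but not tabulated.

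**2. Completers.** The documents use two meanings of completion.

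- *Week 48* (the TEAE definition; Protocol 10.3.3 and 12.1.2). The cut-off is Day 337 + 30 = 367. The scheduled Week 52 visit is 365 − 337 = 28 days later, inside the cut-off. The visit window is Days 351–379; only Days 368–379, a visit 3–14 days late, fall past it. The completer's TEAE window also ends at Week 48, so a lost TEAE must have begun by then, been missed at the Week 48 AE review, and first surfaced at a late follow-up visit.
- *Last study visit* (SAP 2; Protocol 8.3). The cut-off runs from that visit, so nothing reported at it is lost. Taking Day 365, the cut-off is Day 395.

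**3. Telephone contacts for a missed Week 52 visit.** Eight weeks from Day 365 is Days 366–421. On the Week 48 reading, Days 368–421 (54 of 56) are past the cut-off; on the last-visit reading, Days 396–421 (26 of 56). For information held in source only, the cut-off makes no difference: it reaches neither tables nor listings. That conflicts with Protocol 12.1.2 for any event whose onset was in the window.

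**The case against.** Several points on the other side stand, and they limit the finding.

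- A reader might infer that late-reported AEs vanish. They do not: once in the eCRF they stay in the listings, with onset date, seriousness and relation to treatment.
- A reader might infer that scheduled contacts generally miss the cut-off. For completers the scheduled visit meets it, and the last-visit reading of completion, which the SAP itself states, removes the difficulty with that visit altogether.
- It is tempting to turn the calendar into a loss rate: 5 of 14 possible withdrawal days in a dosing interval, or 12 of 29 days in the visit window. These are shares of days, and the documents do not say that withdrawals or visits are spread evenly. A loss also requires that the event was not picked up at the termination visit or in the diary.
- A reader might infer that AEs which caused withdrawal are the ones lost. Those are known at withdrawal and recorded as its reason (Protocol 10.6), so the rule does not remove them.
- The telephone calls are not wholly without use. SAEs learned after completion go on an SAE form within 24 hours, and pregnancies on their own form (Protocol 12.1.2). Calls within the ± 2-week visit window, or to early leavers well before Week 52, are not clearly barred from the eCRF.

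It can also be said that the SAP's word for reporting is loose drafting for occurrence. That may be so, but the sentence as written gives a different count, and the SAP is where it should be settled. Safety is descriptive, with no hypothesis test (SAP 8), and nothing in the documents suggests that the loss would differ between blinded arms.

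**Conclusion.** The contradiction in SAP 8.1 is real. Applied literally, the report-date rule leaves some TEAEs out of the summaries, though not out of the listings. The clearest case is a subject whose withdrawal is recorded 0–4 days after the last dose and who first reports an in-window AE at the 35-day visit. This takes the withdrawal date as recorded and the visit as held on day 35. For completers the loss is small and arises at the follow-up visit only if completion means Week 48 and that visit is 3–14 days late.

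The source-only rule in Protocol 10.3.4 is a separate gap, for non-serious in-window AEs first learned by telephone after the Week 52 visit. Both rules can only lower TEAE counts. The size cannot be computed, because the documents give no event, withdrawal-timing or missed-visit counts. The point is a cheap correction to the safety tables; it does not touch the primary analysis.

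**What to change.** In SAP 8.1:

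- State that any AE with onset or worsening inside the TEAE window is summarised regardless of when it was reported.
- State that AEs with onset after that window and up to the follow-up visit are summarised in the planned follow-up period. This second clause is needed: simply excluding everything with onset outside the TEAE window would drop completers' Week 48–52 events from that period if the window ends at Week 48.
- Define completion as either Week 48 or the last study visit, and use it throughout.
- Reconcile the 30 days with the 4 weeks in Protocol 12.1.2.

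In Protocol 10.3.4, allow eCRF entry, with onset date, of AEs that began up to the end of the follow-up window and are learned by telephone in place of a missed follow-up visit.

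The cost is a few sentences in two documents, a few more eCRF entries from calls that sites already have to make, and possibly slightly higher AE counts.

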8.2 Clinical Laboratory Evaluations

For hematology and clinical chemistry parameters, summary statistics of the value and change from baseline values will be summarized by scheduled study visit for each treatment arm and analysis period (Arm A and B up to Week 16; Arm A, B1 and B2 after Week 16).

Each laboratory test result will be categorized according to the respective reference range as low (below the lower limit), normal (within the reference range), and high (above the upper limit). All laboratory results will be listed by subject and will include the result, reference range, and clinical significance.

Out of range laboratory values will be flagged in the data listings, with the corresponding investigator's judgment of clinical relevance, and a list of clinically significant abnormal values will be presented, as applicable.

The clinical safety and tolerability of the transition from EU RPP to M923 as compared with continuous use of EU RPP with regard to these other safety endpoints will be evaluated over time using descriptive statistics provided over time.

8.3 ECG

Electrocardiogram data (Ventricular rate, PR interval, QRS duration, QT and QT intervals) will be listed with abnormalities indicated. QT interval corrected for heart rate using Fridericia's equation (QTcF) will be calculated as follows: $QTcF = QT / (3\sqrt{RR})$.

8.4 Vital Signs

Vital signs (body temperature, respiratory rate, pulse rate, systolic and diastolic blood pressure and weight) will be listed.

8.5 Physical Examination

Physical examinations (general appearance, head and neck, eyes and ears, nose and throat, chest, lungs, heart, abdomen, extremities and joints, lymph nodes, skin, and neurological), will be listed with abnormalities indicated.

9. EVALUATION OF PHARMACOKINETICS

Secondary PK outcome measures will be analyzed using the PK Analysis set.

For the interim analysis, this will include adalimumab concentration and immunogenicity data through Visit 11, Week 25 and will reflect 5 post-dose assessments on Weeks 8, 16, 17, 21 and 25.

Adalimumab serum levels will be summarized by treatment arm at each scheduled collection. In addition to the usual descriptive statistics, the geometric mean, corresponding 95% confidence interval (CI), and geometric coefficient of variation (CV) will also be presented. Concentrations that are below the limit of quantitation (BLQ) will be replaced with the lower limit of quantitation (LLOQ) for the computation of descriptive statistics. Missing concentrations will be treated as missing. Individual and geometric mean (95% CI) adalimumab concentrations will be graphically presented by treatment (A vs B through Week 16 and versus B1 and B2 following re-randomization).

To evaluate whether anti-adalimumab antibody formation will affect exposure, the summaries will be further stratified by ADA formation (subjects who did not form antibodies, subjects who formed ADAs, subjects who did not form neutralizing ADAs, versus subjects who formed neutralizing ADAs), as appropriate.

Figures will be also be generated to display arithmetic mean adalimumab concentrations versus study week grouped by treatment. Scatterplots and boxplots will also present

adalimumab concentrations stratified by ADA status and to explore the relationship between trough concentrations and ADA titres.

The within-subject variability (geometric CV) in trough concentrations (2 weeks postdose samples) over time (Week 17 to Week 41) will be determined for each subject, which will then be listed, summarized, and compared between treatment arms (EU RPP/EU RPP versus EU RPP/M923) using an analysis of variance model with treatment as a fixed effect. For the subgroup in the EU RPP treatment which is randomized to transition to M923 and back, the troughs

- collected in Weeks 21 and 25 fall into the first transition to M923,
- collected in Weeks 29 and 37 fall into the transition back to EU RPP,
- collected in Week 41 falls into the second transition to M923.

The transition from EU RPP to M923 as compared with continuous use of EU RPP with regard to PK will be evaluated using the descriptive statistics at each schedule time point and statistical comparison of within-subject variability.

Pharmacokinetic data from the study may also be used for population pharmacokinetic/pharmacodynamic analyses. If performed, a separate modelling analysis plan will be prepared and results will be reported separately from the Clinical Study Report.

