9.2 Exclusion Criteria

Subjects who meet **ANY** of the following criteria are not eligible for this study:

1. Presence of forms of psoriasis other than chronic plaque-type (eg, pustular, erythrodermic, or guttate psoriasis)
2. History of or current drug-induced psoriasis (eg, from beta-blockers or lithium).
3. Presence of other skin conditions, including skin infections, which would interfere with assessment of psoriasis
4. Presence of chronic or ongoing medical conditions other than psoriasis for which systemic corticosteroids were used in the last year prior to screening, eg, asthma
5. Presence of other inflammatory conditions other than psoriasis or psoriatic arthritis, eg, rheumatoid arthritis, gout, or inflammatory bowel disease
6. Subject must have no major deviations regarding concomitant medication, such as prior use of systemic TNF inhibitor therapy, investigational or licensed (ie, other investigational biosimilar TNF inhibitor therapy exposure is not permitted), or 2 or more non-TNF biologic therapies required concomitantly
7. Ongoing use of prohibited psoriasis treatments (eg, prohibited topical corticosteroids, systemic corticosteroids, ultraviolet (UV)-therapy including excessive sun exposure, immunosuppressant therapy, including MTX); washout periods detailed in [Section 10.4](#) must be followed
8. Ongoing use of other non-psoriasis prohibited treatments; washout periods detailed in [Section 10.4](#) must be followed

9. All other prior non-psoriasis concomitant treatments must be on a stable dose for at least 4 weeks before baseline
10. Laboratory abnormalities at screening deemed clinically significant by the investigator and/or:
 - a. Hemoglobin < 8 g/dL for women or 8.5 g/dL for men
 - b. White blood cell count < 3.5 x 10⁹/L
 - c. Platelet count < 120 x 10⁹/L
 - d. Aspartate transaminase or alanine transaminase > 1.5 times the upper limit of normal
 - e. Creatinine > 1.5 mg/dL if < 65 years old, or > upper limit of normal if \geq 65 years old
11. Severe, progressive, or uncontrolled renal, hepatic, metabolic, hematologic, gastrointestinal, endocrine, pulmonary, cardiac, or neurologic disease, including pleural effusions or ascites, which in the opinion of the investigator or sponsor pose an unacceptable safety risk
12. History of latex allergy
13. History of or current signs or symptoms or diagnosis of a demyelinating disorder
14. History of or current Class III or IV New York Heart Association congestive heart failure

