10.3.1 Screening and Baseline Assessments

After informed consent has been obtained, subjects will be screened for eligibility based on the inclusion and exclusion criteria defined in [Section 9.1](#) and [Section 9.2](#), respectively. Screening procedures must be done within 28 days of the baseline visit (Visit 2; Week 0).

Screening assessments (Visit 1; Week -4 to baseline) include the following:

- Eligibility evaluation (review of inclusion/exclusion criteria)

- Relevant medical and surgical history and all medications according to the instructions below:
 - Medications/therapies for psoriasis: 8 weeks prior to screening
 - Non-psoriatic medications/therapies: 4 weeks prior to screening
 - All prior biologic medications/therapies (including investigational biologics)
- Review of concomitant medications/non-drug therapies
- TB screening
- sPGA, PASI, BSA evaluation
- Serology tests for HBV, HCV, and HIV-1/HIV-2
- Complete physical examination (see [Section 12.6](#))
- 12-lead ECG (see [Section 12.9](#))
- Vital signs (body temperature, pulse rate, blood pressure, respiratory rate, and measure body weight and height; see [Section 12.8](#))
- Clinical laboratory assessments (hematology and serum chemistry; see [Section 12.7.1](#))
- Urinalysis (see [Section 12.7.2](#))
- Serum pregnancy test (female subjects of childbearing potential only)

At the baseline visit (Visit 2; Week 0), subject eligibility will be confirmed and the following baseline assessments done:

- Patient-reported questionnaires: DLQI and EQ-5D-5L (to be completed prior to any other assessments being done; see [Section 11.2.4](#))
- Eligibility evaluation reviewed (inclusion/exclusion criteria)
- Review of concomitant medications/non-drug therapies
- sPGA, PASI, BSA evaluation (see [Section 11.2.1](#) and [Section 11.2.2](#))
- AE monitoring
- Vital signs (body temperature, pulse rate, blood pressure, respiratory rate, and measure body weight)
- Brief physical examination

- 12-lead ECG
- PK and immunogenicity
- Clinical laboratory assessments (hematology and serum chemistry)
- Urinalysis
- Urine pregnancy test (female subjects of childbearing potential only)

After all baseline assessments have been completed, subjects will be randomized and begin treatment with administration of their first dose of IP as below:

- Randomization of eligible subjects to the following treatment arms:
 - Arm A: M923 from Weeks 0 to 48
 - Arm B: EU RPP from Weeks 0 to 16
- Injection site training

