4.5 Pharmacokinetic (PK) Analysis Set

The PK population will include all subjects who received at least 1 dose of study medication (M923 or EU RPP) and have at least 1 measured concentration at a scheduled PK time point after start of dosing. If any subjects are found to be noncompliant with respect to dosing, a decision will be made on a case-by-case basis and documented as to their inclusion in the analysis. Subjects will be assigned to treatment groups based on treatment actually received.

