HIV = human immunodeficiency virus; EQ-5D-5L = EuroQoL-5 dimensions- 5 levels; PA: posterior-anterior, PASI = Psoriasis Area and Severity Index; PK = pharmacokinetics; PPD = purified protein derivative; sPGA = static Physician Global Assessment; TB = tuberculosis

^a Inclusion/exclusion criteria to be reviewed before randomization. The screening visit needs to occur with enough time prior to randomization to ensure eligibility requirements for the screening visit are met.

^b Concomitant therapy will include pharmacologic and nonpharmacologic therapies.

^c Subjects in Arm B are randomized again at this visit.

^d Subjects will receive testing if not received within previous 3 months and/or doesn't have documented history of prior positive TB test result or active TB infection. Testing includes QuantiFERON, T-SPOT, or PPD and a radiograph or comparable imaging with negative finding for TB or other similar infections (PA or PA and lateral view).

^e sPGA, PASI and BSA assessments should be conducted at screening and at baseline before randomization and study drug administration to ensure eligibility.

^f All subject-completed assessments (ie, patient-reported outcomes) should be completed before any other assessments are done.

Table 3
Schedule of Study Procedures and Assessments

Phase	Screening	Double-Blind Period																		Safety Follow-up ^s
		0	1	4	8	12	16	17	19	21	25	27	29	33	37	39	41	45	48/ETV	
Week	-4 to 0	0	1	4	8	12	16	17	19	21	25	27	29	33	37	39	41	45	48/ETV	52
Study Day	-28 to -1	1	8	29	57	85	113	120	134	148	176	190	204	232	260	274	288	316	337	365
Visit ^r	1	2	3	4	5	6	7	8	9	10	11	12	13	14	15	16	17	18	19	20

^g Complete physical exam will be conducted at screening, Week 16, and 48. All other physical exams will be brief and should include heart, lungs, abdomen and extremities and skin, and any other assessments required to evaluate AEs.

^h ECG should be recorded before blood sampling.

ⁱ Vital signs should be taken before blood sampling. Height will be measured at Visit 1 only.

^j PK and immunogenicity blood samples are to be collected in all subjects at these time points. Samples should be obtained prior to administering study drug if an administration occurs at that visit and before any hematology/chemistry samples to be drawn at that visit.

^k Blood samples will be taken before injection of study drug, after ECG and vital signs assessments, and after PK and immunogenicity sampling if applicable.

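### SAP section 9 sets every below-limit drug concentration to the LLOQ, which reports a drug level before the first dose and biases post-dose means upward by an uncounted amount

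*SAP*

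**What the plan says.** SAP section 9 gives one rule for BLQ concentrations: they "will be replaced with the lower limit of quantitation (LLOQ) for the computation of descriptive statistics". It covers all BLQ values, with no separate treatment of predose samples. The same section states that "Adalimumab serum levels will be summarized by treatment arm at each scheduled collection", and adds the geometric mean with its 95% confidence interval and the geometric CV to the usual statistics. To examine whether antibodies affect exposure, "the summaries will be further stratified by ADA formation".

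PK sampling is among the Week 0 assessments. Protocol section 10.3.1 opens that list with "At the baseline visit (Visit 2; Week 0), subject eligibility will be confirmed and the following baseline assessments done" and follows it with "After all baseline assessments have been completed, subjects will be randomized and begin treatment with administration of their first dose of IP as below". The footnote to the SAP section 15.2 schedule agrees: "Samples should be obtained prior to administering study drug if an administration occurs at that visit". Protocol section 9.2 excludes "prior use of systemic TNF inhibitor therapy, investigational or licensed".

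The PK analysis set (SAP section 4.5) requires that a subject "have at least 1 measured concentration at a scheduled PK time point after start of dosing". That condition selects subjects; it does not remove the Week 0 records of those selected. The protocol's PK sections (11.3 and 13.4.4.3) contain no BLQ rule that would override the SAP's. Neither document gives the LLOQ, asks for the number of BLQ values, or plans a sensitivity analysis for how they are handled.

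**The concern.** The LLOQ is the upper bound of what a BLQ sample can contain, so replacing BLQ values with it errs in one direction only.

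Before the first dose this is a plain misstatement. Subjects with no prior TNF inhibitor should have no adalimumab in serum, yet the table would show a positive level in every arm.

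After dosing, the error depends on how many values are BLQ, and the planned tables would not show that number. Exposure is a secondary outcome, and the ADA-stratified summaries exist to show whether antibodies reduce it. If they do, BLQ values will be commoner in the ADA-positive stratum. The upward bias will then be larger there, and the contrast will look smaller than it is.

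**Working it through.** The documents state no figure on this point, so there is none to reproduce. The check is algebra, with the LLOQ taken as 1 unit.

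**Inputs from the documents.** The substitution rule and the summary at every scheduled collection (SAP section 9); a predose PK sample at Week 0 (Protocol section 10.3.1; SAP section 15.2); no prior TNF inhibitor (Protocol section 9.2).

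**Inputs assumed.** The BLQ share f, and lognormal levels with log-SD σ of 1 to 2. None of these is in the documents.

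**Week 0.** If every value is BLQ, every value becomes 1 × LLOQ. Then arithmetic mean = geometric mean = 1 × LLOQ, SD = 0 and geometric CV = 0%, where the expected level is 0.

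**Post-dose geometric mean.** Let z be the standard normal quantile at f and φ the normal density. Replacing the lower fraction f of a lognormal sample with the LLOQ raises the mean of the logs by σk, where k = zf + φ(z). The geometric mean is therefore multiplied by exp(σk). LLOQ/2 in place of the LLOQ multiplies this further by 2^(−f).

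| f | z | φ(z) | k | LLOQ rule, σ = 1 | LLOQ rule, σ = 2 | LLOQ/2, σ = 1 | LLOQ/2, σ = 2 |
|---|---|---|---|---|---|---|---|
| 2% | −2.054 | 0.0484 | 0.0073 | +0.7% | +1.5% | −0.6% | +0.1% |
| 5% | −1.645 | 0.1031 | 0.0209 | +2.1% | +4.3% | −1.4% | +0.7% |
| 10% | −1.282 | 0.1755 | 0.0473 | +4.8% | +9.9% | −2.2% | +2.6% |
| 30% | −0.524 | 0.3477 | 0.1904 | +21% | +46% | −2% | +19% |
| 50% | 0 | 0.3989 | 0.3989 | +49% | +122% | +5% | +57% |

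Example, f = 30%, σ = 1: k = −0.5244 × 0.30 + 0.3477 = 0.1904, and exp(0.1904) = 1.21.

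**Spread.** At f = 30% the SD of the logs after substitution is 0.751σ, about 25% too small, so the geometric CV is understated as well.

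**Arithmetic mean.** Compared with setting BLQ to 0, the rule adds f × LLOQ. With a geometric CV of 60% among quantifiable values, the inflation runs from 0.2% (f = 10%, quantifiable geometric mean 50 × LLOQ) to 51% (f = 75%, 5 × LLOQ). It is small when levels lie far above the LLOQ.

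**ADA contrast, illustration only.** Take an ADA-positive stratum with f = 0.50 and quantifiable geometric mean 10 × LLOQ, and an ADA-negative stratum with f = 0.02 and 50 × LLOQ. With c as the value assigned to BLQ samples, the ratio of geometric means is (10^0.50 × c^0.50) / (50^0.98 × c^0.02). This gives 0.068 at c = LLOQ, 0.049 at LLOQ/2 and 0.023 at LLOQ/10. The LLOQ rule gives the ratio nearest to 1, that is, the weakest apparent ADA effect.

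**Per-subject trough CV, if the rule were applied there.** Five troughs all BLQ give CV = 0%. Troughs of 5, 4 and 3 × LLOQ plus two BLQ give 90% under the LLOQ rule and 164% under LLOQ/2.

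**The case against.** Several points on the other side have weight.

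- **Week 0 has little consequence.** A column of identical values with SD 0 is recognizable as a floor. No planned comparison uses Week 0, and the interim PK text names five post-dose assessments only. This stands as to impact. It does not take Week 0 out of the summaries at each scheduled collection.
- **The size is assumed.** This stands. The BLQ shares and log-SDs are assumptions, and at 2-5% BLQ the error is only about 1-4%.
- **Other displays help.** Medians and ranges are planned, as are subject listings, individual concentration plots, and scatterplots and boxplots by ADA status. The median is unaffected while fewer than half the values are BLQ. None of these corrects the geometric mean or reports the BLQ count.
- **Nothing confirmatory depends on it.** SAP section 5 limits formal hypothesis testing to the primary outcome, so the equivalence conclusion does not rest on this rule.

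Two stronger readings are tempting. First, a reader might infer that exposure in ADA-positive subjects will be inflated as a matter of fact. The documents contain no concentrations by ADA status, and whether antibodies lower exposure is the question the SAP poses. The claim must stay conditional.

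Second, a reader might infer that the rule feeds the analysis of variance comparing per-subject trough CV between Arms B1 and B2, so that subjects with very low exposure score as perfectly stable. SAP section 9 confines the rule to descriptive statistics and does not say how BLQ troughs enter that CV. A CV of zero would in any case need every trough to be BLQ. The PK set might also exclude a subject who is BLQ at every post-dose visit, depending on whether a measured concentration means a quantifiable one. What remains is an ambiguity to close.

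**Conclusion.** The point holds as a minor but clear defect in the PK summaries. As written, the plan reports a drug level of 1 × LLOQ with SD 0 before any drug has been given, and no other section corrects it. That part needs only the expectation that predose samples in TNF-inhibitor-naive subjects are BLQ.

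After dosing the direction is certain: means and geometric means can only be biased upward. The size is not known. The range runs from about 1% at 2% BLQ to 122% at 50% BLQ, and it rests on the lognormal assumption with log-SD 1 to 2.

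That the rule understates the ADA effect follows only if ADA-positive subjects have more BLQ values. An effect on the B1 versus B2 variability comparison is not established.

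**What to change.** Amend SAP section 9 as follows.

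1. Treat predose Week 0 BLQ values as zero or not quantifiable, and leave them out of geometric means.
2. Report n (%) BLQ by visit, arm and ADA stratum.
3. For post-dose geometric means and CVs, use either a left-censored lognormal estimate or LLOQ/2 as the main method, with the other as a sensitivity analysis. Where a stratum is all or nearly all BLQ, report only the count, since the censored model cannot estimate it.
4. State whether the BLQ rule applies to the per-subject trough CV. If it does, report by arm how many subjects have some or all troughs BLQ, and show the B1 versus B2 comparison with and without the all-BLQ subjects. Simply excluding them would remove subjects from a randomized comparison on a post-randomization outcome.

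The cost is SAP wording and minor programming; no new data are needed. The drawback is a model-based estimate in place of a plain mean, resting on a lognormal lower tail that cannot be observed. LLOQ/2 is simpler but not unbiased: in the table it errs by up to +57% at 50% BLQ with log-SD 2. This is why both should be shown beside the BLQ counts.
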